3.3.2 Total Number of Study Sites/Total Number of Subjects Projected

All testing procedures and interventions will occur in the Center for Rehabilitation at CHOP. Sixty participants with CP between the ages of 1-3 years will be recruited for the study. It is expected that enrollment of 60 participants will produce 42 evaluable datasets.

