6.2.2 Efficacy Analysis

For the analysis of Aim 1, Hypothesis 1.1 (*Gross motor ability will exceed predicted values after DSM treatment and gains will be maintained at follow-up*), GMFCS percentile ranks will be obtained after 6, 12, 18 and 24 weeks of treatment based on actual GMFM-66

scores and age, and will be compared to predicted percentile ranks based on age and initial GMFM-66 score. Mean values and 95% confidence intervals will be calculated for actual and predicted scores. Optimal treatment duration will be identified as the maximum change observed at the related time point which is maintained during the following period. If maximum change occurs after 24 weeks, this time will be considered the optimal duration. Spearman correlation will be utilized to analyze Hypothesis 1.2 (*Outcomes will be related to the amount of error, variability and engagement during treatment*), to estimate the relationship between motor improvement and the amount of motor error, variability and engagement experienced during treatment.

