To address Aim 2, Hypothesis 2.2 (*Participants who receive DSM treatment will demonstrate greater improvements than participants who receive CONV treatment, and the differences will be maintained at follow-up*) will be analyzed by comparing GMFM-66 outcomes between participants receiving DSM treatment and those receiving CONV treatment. Baseline characteristics in each group will be compared using two-sample tests, including t-tests, the Mann-Whitney test, and chi-square tests, as appropriate for the respective type of data. We will then use a univariate approach for comparing the two treatments using analyses of variance and covariance (ANCOVA). Measurements at 6, 12, 18 and 24 weeks, as well as at both follow-up points after treatment will be individually compared between the two treatment conditions using baseline score, cognition and caregiver self-efficacy as covariates. We will also use a multivariate approach using linear mixed effects model⁵⁹ or the Generalized Estimating Equation (GEE).⁶⁰ The advantage of using the mixed effects model or the GEE approach is that they will not drop subjects from the analysis due to not having measurement at any of the post-treatment time points. Also, such analyses will allow us to examine the between subjects effects which represent a factor with two levels (treatment conditions) and within subjects effects which represent time effects (pre and post measurements) and a time by condition interaction. The random effect model will be implemented utilizing SAS Proc Mixed and the GEE will be implemented by SAS Proc Genmod. (SAS/STAT User's Guide, 2004, Version 9. Cary, NC: SAS Institute, Inc). Cognition and caregiver self-efficacy will be included as covariates in these analyses. Two-sided p values of less than 0.05 will be considered statistically significant. Similar procedures will be used for the analysis of secondary outcomes, with appropriate tests for parametric (postural control, physical activity) and non-parametric measures (caregiver satisfaction, Child Engagement in Daily Life).

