6.3 Sample Size and Power

This is a proof of concept futility study and to keep the number of participants to the minimum necessary, sample size estimation was not driven to achieve a specific effect size or statistical power, but rather to derive estimates and confidence intervals. A minimum of 15 subjects receiving a novel treatment has been recommended for early studies of dose-response and futility in neurorehabilitation.⁵¹ We also calculated predicted change and 95%

confidence intervals for both treatments. Predicted change after DSM treatment was determined from the data of the four pilot children who would meet the proposed selection criteria. A mean GMFM-66 increase of 5.3 was observed after six weeks of treatment. Assuming such change will be doubled after 12 or more weeks of treatment, a 10.6 increase from baseline is predicted as a minimum change after DSM treatment. Predicted change after CONV treatment was determined from maximum change in published GMFM-66 scores over six months in a 24 month old child classified as GMFCS level II.⁵⁵ A 1.8 increase from baseline is predicted after CONV treatment. We estimated that with a sample size of 17 participants receiving each treatment, a 2-sided 95% confidence interval for the difference in GMFM-66 will extend +/- 6 from the observed difference assuming that the common standard deviation (SD) is 9 (nQuery Advisor 6.0), which was larger than observed in the pilot data for a conservative estimate. An additional 8 children (4 in each group) will be enrolled to account for an anticipated attrition rate of 20%. Based on random assignment, 21 participants will receive DSM treatment, and another 21 will receive CONV treatment.

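### The Aim 1 duration rule rests on visit-wise means with no missing-data method, so dropout of children with low gains could tilt the choice towards 24 weeks

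*Combined protocol and SAP*

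**What the plan says.** Aim 1 (Section 2.1) is to find the optimal duration of DSM treatment between 6 and 24 weeks. The method is in Section 6.2.2. "GMFCS percentile ranks will be obtained after 6, 12, 18 and 24 weeks of treatment", and these are compared with ranks predicted from age and initial score. "Mean values and 95% confidence intervals will be calculated for actual and predicted scores". The decision rule follows: "Optimal treatment duration will be identified as the maximum change observed at the related time point which is maintained during the following period". For the last visit it adds: "If maximum change occurs after 24 weeks, this time will be considered the optimal duration". No longitudinal model, analysis set or treatment of missing visits is given for this aim.

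For Hypothesis 2.2 the same section does more: "We will also use a multivariate approach using linear mixed effects model", or alternatively GEE. The stated advantage is that "they will not drop subjects from the analysis due to not having measurement at any of the post-treatment time points".

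Attrition is expected. Section 6.3 says "An additional 8 children (4 in each group) will be enrolled to account for an anticipated attrition rate of 20" per cent, and Section 3.3.2 says "It is expected that enrollment of 60 participants will produce 42 evaluable datasets". Section 4.4.1 gives children who withdraw the Assessment 5 procedures as an early termination visit. It does not say how those scores enter the Aim 1 means.

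**The concern.** The rule compares 6, 12, 18 and 24 weeks with one another, so anything that shifts one visit's mean relative to the others can change the answer. If each mean uses the children present at that visit, and those with low gains are more likely to have left, the later means rise through the change in who is measured. The rule would count that rise as benefit of longer treatment.

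The plan's own expectation makes the rule sensitive to this. Section 6.3 assumes a single gain of 10.6 for 12 or more weeks, and Section 1.3 speaks of an anticipated plateau. If that is right, the true differences between 12, 18 and 24 weeks are zero and a modest artefact can settle the choice. The maintenance condition offers little protection at the visit most affected, because the sentence on 24 weeks states no such condition. At stake is the duration carried forward from a primary aim.

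**Working it through.** **Inputs.** From Section 6.3: 21 DSM children, 17 after attrition, SD 9, gain 5.3 at 6 weeks and 10.6 from 12 weeks on. From Section 3.3.2: 60 enrolled, 42 evaluable. From Section 1.3: net changes of 2.4 to 9.7 in four pilot children after six weeks.

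**The plan's own figure.** The half-width of the 95% interval for the between-group difference is 1.96 × 9 × √(2/17) = 6.05 (6.29 with the t distribution). The stated ±6 is reproduced. The plan gives no figure for the Aim 1 choice.

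**Expected loss.** Section 6.3: 4/21 = 19%. Section 3.3.2: (60 − 42)/60 = 30%, or 9 of 30 per arm.

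**Shift in a visit mean.** Let a be the mean change of the 17 completers and b the mean change the 4 dropouts would have had. The full-group mean is (17a + 4b)/21, so the completers' mean exceeds it by a − (17a + 4b)/21 = 4(a − b)/21.

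| Assumed gap a − b | 4 of 21 lost | 9 of 30 lost |
|---|---|---|
| 3 | 0.57 | 0.90 |
| 5 | 0.95 | 1.50 |
| 7 | 1.33 | 2.10 |

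The gaps are assumptions. A gap of 7 is close to the whole pilot spread (9.7 − 2.4 = 7.3). The extreme case, in which exactly the lowest responders leave, gives 3.0 points (4 of 21) or 4.5 points (9 of 30) with normal data and SD 9.

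**Effect on the choice.** The DSM arm was simulated at the four visits, 3,000 runs per scenario. Assumptions not in the documents: SD 9 applies to the change at each visit; within-child correlation is 0.8; dropout is spread over the three later intervals; the odds of leaving rise by a factor of e to e² per SD lower observed gain. GMFM-66 change stood in for percentile rank. The largest mean was picked without the maintenance condition, which the plan does not define numerically. The likelihood estimate is one that is valid when dropout depends on observed scores. Entries are the share of runs that pick 24 weeks.

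| True mean change at 6, 12, 18, 24 weeks | Lost | Visit means | Likelihood estimate | Complete data |
|---|---|---|---|---|
| 5.3, 10.6, 10.6, 10.6 | 4 of 21 | 56–68% | 33–36% | 32–34% |
| 5.3, 10.6, 10.6, 10.6 | 9 of 30 | 66–74% | 35–36% | 34% |
| 5.3, 10.6, 10.1, 9.6 | 4 of 21 | 38–46% | 15–17% | 12–13% |
| 5.3, 10.6, 10.1, 9.6 | 9 of 30 | 46–56% | 15–16% | 11% |

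On the plateau with 4 of 21 lost, the 24-week visit mean averaged 11.8 to 12.6 against a true 10.6, while the likelihood estimate averaged 10.5 to 10.6. That shift of 1.2 to 2.0 corresponds to gaps of roughly 1.2 × 21/4 = 6.3 to 2.0 × 21/4 = 10.5. The simulated dropout is therefore near or above the top of the 3 to 7 range.

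**Dropout unrelated to response.** On the plateau, visit means picked 24 weeks in 34% (4 of 21) or 36% (9 of 30) of runs, and the 24-week mean was not shifted (10.5 and 10.6). The tilt comes from selective dropout, not from attrition as such.

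**The case against.** The strongest reply is that a reader might take Section 6.2.2 to say that different children are compared at different visits, and it does not. It never says who enters each mean. The evaluable counts in Sections 3.3.2 and 6.3 could be read as one fixed set, and the change of sample between visits would then disappear. This stands as a limit on the claim. With no model or imputation named, the children observed at each visit remain the natural reading. A completers-only set would itself be selected and would overstate gains at every visit.

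Other parts also stand. The attrition is not said to fall before week 24: participation lasts 18 months, 12 of them follow-up, so 21 against 17 is an upper illustration and fewer early losses shrink the shift. Sections 3.1.2 and 4.4 keep poorly adherent children in the study, although they do not say how missing scores are handled. Early termination scores, if placed at week 24, would put leavers back into that mean and could change the direction of the bias.

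A shift of 0.6 to 1.3 is also small beside sampling error. The standard error of a visit mean is 9/√17 = 2.2, and that of a paired visit difference with correlation 0.8 is 9 × √0.4/√17 = 1.4. But the rule picks the largest point value and does not weigh standard errors, so a systematic shift matters where true differences are near zero. The model removes the tilt but not the imprecision: on a plateau even complete data divide the choice about evenly among 12, 18 and 24 weeks.

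**Conclusion.** The concern holds in a conditional form. The Aim 1 choice rests on visit-wise means with no missing-data method, in a plan that expects 19% to 30% loss and already gives a reason to use a longitudinal model for Aim 2. If children with low observed gains leave before week 24, the choice tilts towards 24 weeks. The conclusion depends on each mean using the children observed at that visit, on the assumed gaps, and on losses before week 24.

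Two stronger readings go too far. A reader might infer that a finding in favour of 24 weeks would be an artefact. Nothing in the documents says that poor responders leave, and without selective dropout there is no bias. A reader might also infer that the Aim 2 analysis can be carried over unchanged. It allows GEE, which in ordinary unweighted form does not handle response-related dropout, and it compares GMFM-66 between arms, whereas Aim 1 compares actual with predicted percentile ranks. The analysis should be changed before the data are examined; it does not undermine the trial.

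**What to change.** In Section 6.2.2, under Hypothesis 1.1:

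- Estimate the visit-specific changes used in the duration rule from a linear mixed model, not unweighted GEE. Treat visit as a category and fit the model to actual-minus-predicted values (percentile rank or GMFM-66; state which), using all available visits of all randomised DSM children.
- Keep the maintenance condition and apply it to the model estimates.
- Enter early termination assessments at their actual time, not as week 24.
- Show a completer-only curve as a check.

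The cost is a short model specification, with a model class and software already named in the section. The model relies on missing at random, which is weaker than what observed-case means need, but it does not protect against dropout that depends on unseen scores.

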2 STUDY OBJECTIVES

2.1 Primary Objectives (or Aims)

Aim 1. To determine the optimal treatment duration of dynamic supported mobility (DSM) treatment in infants and toddlers with cerebral palsy, between 6 to 24 weeks of treatment.

Hypothesis 1.1. Gross motor ability (measured by the GMFM-66) will exceed individual predicted values in infants and toddlers with cerebral palsy after 12, 18, and 24 weeks of DSM treatment, and gains will be maintained at 3, 6 and 12 month follow-up points.

Hypothesis 1.2. Gross motor function gains will be positively related to the amount of motor error, variability and engagement experienced during DSM treatment.

Aim 2. To determine the futility of dynamic supported mobility compared to conventional rehabilitation in infants and toddlers with cerebral palsy.

Hypothesis 2.1. The frequency of adverse events among participants who receive DSM treatment and those who receive conventional (CONV) treatment will not differ by greater than 10 percent.

Hypothesis 2.2. Participants who receive DSM treatment will demonstrate significantly greater improvements in gross motor ability (measured by the GMFM-66) than participants who receive equal amounts of CONV treatment, and these differences will be maintained at each follow-up point.

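### H1.1 compares each DSM child with that child's own prediction, but the plan gives separate intervals for actual and predicted scores and none for the paired difference

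*Combined protocol and SAP*

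**What the plan says.** Section 2.1 (Primary Objectives) words Hypothesis 1.1, under Aim 1, as follows: "Gross motor ability (measured by the GMFM-66) will exceed individual predicted values in infants and toddlers with cerebral palsy". The hypothesis covers 12, 18 and 24 weeks of DSM treatment, and adds that gains hold at the 3, 6 and 12 month follow-ups.

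Section 6.2.2 (Efficacy Analysis) says how this will be examined. GMFCS percentile ranks reached during treatment "will be compared to predicted percentile ranks based on age and initial GMFM-66 score". The next sentence is the only statistical specification of that comparison: "Mean values and 95% confidence intervals will be calculated for actual and predicted scores".

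The section then gives a separate rule for the optimal duration, based on the largest observed change that is sustained through the next period. The ANCOVA, the mixed model or GEE, and the significance rule ("Two-sided p values of less than 0.05 will be considered statistically significant") all come in the paragraph on Aim 2, DSM against conventional treatment, which extends similar procedures to the secondary outcomes.

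**The concern.** H1.1 asks whether children do better than their own predictions. Actual and predicted values belong to the same children, and the prediction starts from the child's own baseline, so the two are likely to be positively correlated. The uncertainty of the mean difference depends on that correlation. An interval for the mean actual value and another for the mean predicted value do not contain it, so the interval that answers H1.1 cannot be recovered from what the plan would report.

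Set side by side, two overlapping intervals invite the conclusion that no gain over prediction was shown, even where the paired interval would exclude zero. Section 6.3 says the study was sized to yield estimates and confidence intervals, so the missing interval matters.

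**Working it through.** **Inputs**

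- Pairing: section 6.2.2, prediction from the same child's age and initial score.
- Number of DSM children: 17 completers or 21 enrolled (section 6.3: "21 participants will receive DSM treatment, and another 21 will receive CONV treatment").
- SD: 9 GMFM-66 points (section 6.3: "assuming that the common standard deviation (SD) is 9 (nQuery Advisor 6.0), which was larger than observed in the pilot data"). The text does not say whether this is the SD of scores or of change. No SD is given for percentile ranks.
- Correlation r between actual and predicted: not in the documents. Assumed, and varied from 0 to 0.9.

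**Step 1: the plan's own precision figure.** Section 6.3 states that "with a sample size of 17 participants receiving each treatment, a 2-sided 95% confidence interval for the difference in GMFM-66 will extend +/- 6". Check: 1.96 × 9 × sqrt(2/17) = 6.05; with t on 32 df, 6.29. The figure reproduces, but it concerns two independent arms. The documents give no precision figure for H1.1.

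**Step 2: separate intervals.** Each half-width is t(n−1) × SD/sqrt(n).

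- n=17: 2.12 × SD/sqrt(17) = 0.514 SD. Two such intervals separate only if the means differ by 2 × 0.514 = 1.03 SD.
- n=21: 2.086 × SD/sqrt(21) = 0.455 SD. Separation needs 0.91 SD.

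**Step 3: paired interval.** With equal SDs the half-width is t(n−1) × SD × sqrt(2(1−r)/n).

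**Step 4: ratio of the two.** With equal SDs, the separation threshold divided by the paired half-width is sqrt(2/(1−r)), whatever the sample size or scale. With SDs s1 and s2 it is (s1+s2)/sqrt(s1² + s2² − 2·r·s1·s2). If the predicted SD is half the actual SD, this becomes 1.5/sqrt(1.25 − r).

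| r | Paired half-width, n=17 | Paired half-width, n=21 | Ratio, equal SDs | Ratio, predicted SD half of actual |
|---|---|---|---|---|
| 0 | 0.73 SD | 0.64 SD | 1.41 | 1.34 |
| 0.5 | 0.51 SD | 0.46 SD | 2.00 | 1.73 |
| 0.7 | 0.40 SD | 0.35 SD | 2.58 | 2.02 |
| 0.8 | 0.33 SD | 0.29 SD | 3.16 | 2.24 |
| 0.9 | 0.23 SD | 0.20 SD | 4.47 | 2.54 |

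If a reader instead compared the two means as independent samples (±6.29 at n=17, SD 9), the ratio to the paired half-width would be 0.96 at r=0, 1.36 at 0.5, 2.15 at 0.8 and 3.04 at 0.9.

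**Step 5: illustration in GMFM-66 points.** Take SD 9 for both quantities and n=17. Each separate interval is ±4.63, so separation needs 9.25 points. The paired half-width is 6.54 at r=0 and 2.93 at r=0.8. Section 6.3 predicts a DSM gain of 10.6 and takes a gain of 1.8 from published scores: 10.6 − 1.8 = 8.8. A difference of that size would leave the separate intervals overlapping (8.8 < 9.25), while the paired interval would exclude zero even at r=0 (8.8 − 6.54 = 2.26). With 21 children the separation threshold is 8.19, which 8.8 just clears. This is only an illustration: the plan compares ranks, and 1.8 is its prediction for the conventional arm, not a prediction for each child.

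**The case against.** A reader might infer that H1.1 is to be decided by whether the two intervals overlap, and so that the plan adopts a yardstick several times too wide. The documents do not support that. Section 6.2.2 says the ranks will be compared and lists means and intervals; it gives no overlap rule and no other criterion. The comparison could even be meant child by child. This objection stands: the ratios describe one possible reading, not a stated procedure.

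The size is also uncertain. Eligibility requires pulling to stand and excludes independent walkers, which narrows baseline scores and could make predicted values less variable than actual ones. Section 1.1 notes that GMFCS level is less stable before age 2, so a high correlation in ranks cannot be taken for granted. Percentile ranks are bounded, and neither their SD nor their correlation is given. This stands too, and is why a range is shown.

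A reader might also infer that the Aim 1 choice of duration is compromised. It is not: that rule uses the largest sustained change and neither interval. Nor do the documents show that the comparison must move to GMFM-66 points with GMFCS level fixed at baseline; that is a separate choice.

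Finally, this is an exploratory estimation study, and an overlap reading errs on the cautious side. Both are true, so no formal test need be added. Neither supplies the missing interval.

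**Conclusion.** The point holds in limited form. H1.1 is a within-child contrast, and the only intervals planned for it are two marginal ones that cannot give the precision of that contrast. The Aim 2 models and significance rule do not fill the gap.

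If the intervals were read by overlap, the yardstick would be 1.4 times too wide at r=0, 2.0 at r=0.5, 3.2 at r=0.8 and 4.5 at r=0.9. These figures assume equal SDs and a correlation that the documents do not give. Unequal SDs reduce them, for example to 2.2 at r=0.8 if the predicted SD is half the actual. The ratios carry over to percentile ranks; the point values do not. The consequence is confined to the H1.1 statement that actual exceeds predicted.

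**What to change.** In section 6.2.2, add that at each treatment and follow-up assessment, actual minus predicted percentile rank will be computed for each DSM child, and that the mean paired difference will be reported with its 95% CI. State that the H1.1 conclusion rests on that interval. The separate means and intervals can stay as description. The same difference in GMFM-66 points, the scale in which H1.1 is worded, may be reported as well.

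The cost is a sentence or two of analysis text. The ranks are already to be derived from GMFM-66 scores and ages, and the GMFM-66 is already scheduled at every assessment, so no new data, visits or participants are needed.

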The best opportunity to maximize lifelong independence is early in motor development when the differences in motor skill between functional levels are relatively small and there is the most potential for neuroplastic change. Gross motor function plateaus by 4-7 years of age¹³ after which motor ability is relatively fixed with large skill gaps between levels. In fact, the Gross Motor Function Classification System (GMFCS)⁶ of motor severity remains relatively stable throughout childhood and adulthood,^{14,15} regardless of treatment. *However, the early years of life are an exception* with less stability in GMFCS classifications before the age of 2 years.¹⁶ There is also growing evidence of a critical period of neuroplasticity for motor control centers in the brain. Similar to the development of sensory systems, recent work has confirmed that plasticity in the motor system is both activity-dependent, and more robust in early as compared to later years.^{17,18} Moreover, maladaptive changes that occur after central nervous injury are difficult to reverse once established.¹⁹ These observations suggest that there is a window of opportunity for interventions applied *prior* to nearing the developmental peak to improve the trajectory of motor development and reduce lifelong physical disability.

How best to optimize motor ability during this narrow window remains unknown. Current practice does not reflect key learning principles of typical motor development. Typical toddler movement is characterized by a high degree of motor exploration, error and movement variability, which are critical factors in the refinement of motor control. Infants and toddlers with CP often cannot create these experiences on their own, losing natural opportunities to learn more coordinated movements and establish the associated neural pathways that control skilled movement. In contrast to their typically-developing peers, young children with CP instead repeatedly practice poorly-controlled motor patterns. Our work will investigate a promising novel treatment designed to allow infants and toddlers with CP to create for themselves motor learning experiences more similar to their typically developing peers. This contribution will be significant because the treatment may have the potential to improve the trajectory of motor development and reduce lifelong physical disability in individuals with CP. The work will increase our understanding of how best to

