3.1.3 Follow-up Phase

The treatment phase will end after 24 weeks of treatment. Three follow-up assessments will occur at 3, 6 and 12 months after treatment ends.

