4.2.2 Treatment sessions 1-72

- Rehabilitation (three 30-minute sessions per week of either DSM or CONV treatment)
- Possible video or photograph

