6 STATISTICAL CONSIDERATIONS

6.1 Primary Endpoint

The primary endpoint will be the change in GMFM (Gross Motor Function Measure) from baseline to each post-treatment assessment session.

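### The Aim 1 rule can find at most a time to plateau under continuous DSM: no child is planned to stop before week 24, and a maximum at week 24 is called optimal

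*Combined protocol and SAP*

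**What the plan says.** Aim 1 (Section 2.1) sets out to find the optimal DSM duration "between 6 to 24 weeks of treatment". The decision rule is in Section 6.2.2: "Optimal treatment duration will be identified as the maximum change observed at the related time point which is maintained during the following period". It is followed by: "If maximum change occurs after 24 weeks, this time will be considered the optimal duration".

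The treatment schedule is the same for all. Section 4.2.2 lists sessions 1 to 72 as "Rehabilitation (three 30-minute sessions per week of either DSM or CONV treatment". Section 3.1.3 says "The treatment phase will end after 24 weeks of treatment" and "Three follow-up assessments will occur at 3, 6 and 12 months after treatment ends".

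Two scales are available for *change*. Section 6.1 says "The primary endpoint will be the change in GMFM (Gross Motor Function Measure) from baseline to each post-treatment assessment session". The paragraph of Section 6.2.2 that holds the duration rule first compares actual GMFCS percentile ranks with ranks predicted from age and initial score. The rule does not say which scale applies, whether follow-up visits count, or how much loss still counts as maintained.

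**The concern.** Aim 1 is a primary aim, and the trial is meant to inform Phase III. Three features of the rule could produce a wrong conclusion even if it is followed exactly.

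- A shorter course could be reported as optimal and lasting although no group received that course and then stopped.
- Twenty-four weeks could be reported as optimal when the children were simply still improving. Section 1.3 argues for following response until it levels off before Phase III, but the rule has no outcome for a response that has not levelled off.
- On raw scores, ordinary development could be read as benefit from longer treatment. Section 1.1 says "Gross motor function plateaus by 4-7 years of age". A child enrolled at the upper age limit of 36 months is about 36 + 6 = 42 months old, or 3.5 years, when treatment ends.

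**Working it through.** **Schedule against rule (no arithmetic needed).**

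| Candidate duration | What follows it for DSM children | What *maintained* can mean |
|---|---|---|
| 6, 12 or 18 weeks | further DSM sessions | maintained while still treated |
| 24 weeks | visits 3, 6 and 12 months after treatment | maintained after stopping |

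Withdrawals do not fill the gap. They are self-selected, and Section 4.4.1 gives them one early termination visit.

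**The last sentence.** *After 24 weeks* can mean at the week 24 visit or later. Either way 24 weeks is named.

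**The plan's own figure.** Section 6.3 gives a 95% confidence interval half-width of 6 for the between-arm difference, with 17 per arm and SD 9. Check: 1.96 × 9 × √(2/17) = 6.05 (6.29 with t on 32 df). The figure reproduces, but it concerns the between-arm difference. The plan gives no operating figure for the duration rule.

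**Simulation of the rule.** Inputs from Section 6.3: a gain of 5.3 at six weeks, 10.6 from 12 weeks, a 1.8-point rise over six months without DSM, SD 9, and n = 17 (evaluable) or 21 (randomised). Assumptions: DSM adds nothing after week 12; growth is linear at 1.8 per 26 weeks; inter-visit correlation is 0.80 to 0.98, autoregressive or exchangeable.

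Expected raw change is the DSM effect + 1.8 × week/26:

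- week 6: 5.3 + 0.42 = 5.72
- week 12: 10.6 + 0.83 = 11.43
- week 18: 10.6 + 1.25 = 11.85
- week 24: 10.6 + 1.66 = 12.26

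The expected maximum is at week 24 although the DSM effect stopped growing at week 12. Share of 100,000 simulated trials per setting in which the maximum leads to 24 weeks:

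| Scale of change | Four treatment visits | Follow-up maxima counted as 24 weeks |
|---|---|---|
| Raw GMFM-66 | 52% to 85% | 96% to 100% |
| Expected growth removed | 33% to 38% | 62% to 67% |

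With growth removed and four visits, 12 weeks is also named in 33% to 38%. There is then no push to 24 weeks, but the choice among 12, 18 and 24 weeks is close to random.

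**Precision of one 6-week block.** On the same assumptions, the SD of a block gain is 9 × √(2(1 − ρ)): 5.69 at ρ = 0.80 and 1.80 at ρ = 0.98. With 17 children the one-arm 95% half-width is 2.12 × 5.69/√17 = 2.9, or 2.12 × 1.80/√17 = 0.9. For DSM minus CONV it is 2.04 × 5.69 × √(2/17) = 4.0, or 2.04 × 1.80 × √(2/17) = 1.3.

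**The case against.** The strongest reply is that Aim 1 already adjusts for age. The paragraph containing the rule compares actual with predicted percentile ranks, Hypothesis 1.1 speaks of exceeding individual predicted values, and Section 3.1 asks whether the predicted trajectory is altered. This stands. A reader might infer that the rule is biased towards 24 weeks whatever scale is used. The documents do not support that: the push needs raw change, and the rule leaves the scale open.

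The size is also assumption-bound. The simulation takes the largest mean and does not model the *maintained* condition, for which no tolerance is given. With independent visit noise, n = 21 and growth of 0.45 per six weeks, the share for week 24 is 93% at SD 1, 51% at SD 5 and 43% at SD 9. If *maximum change* meant the largest gain per block, linear growth would add equally to every block and there would be no pull.

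A reader might also infer much faster growth from the pilot by dividing the mean gain by the smallest rate ratio in Section 1.3: 5.3/3.8 = 1.39 per six weeks. That pairs a mean with an individual extreme. The other end gives 5.3/15.1 = 0.35, below the 0.45 (1.8/4) used above.

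Finally, Aim 1 declares a range of 6 to 24 weeks, so 24 weeks may be the best within that range. That is fair as a description of the range tested. It does not make the upper limit an optimum when scores may still be rising.

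**Conclusion.** Two parts hold without any simulation. The trial can show at most the time to plateau under continuous DSM, with retention after stopping seen only for the 24-week course. And the rule labels 24 weeks optimal in the pattern that signals no plateau.

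The third part is conditional. On raw GMFM-66 change, with a true 12-week plateau, 24 weeks is named in about 52% to 85% of trials over the four treatment visits, against about a third without growth. This rests on linear growth of 1.8 points per 26 weeks, SD 9 and an assumed correlation of 0.80 to 0.98. On the age-referenced comparison the push largely disappears, though a lean to 24 weeks (62% to 67%) returns if follow-up maxima count. The rule as written should be amended.

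**What to change.** In Section 6.2.2 and Aim 1:

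1. Apply the duration rule to the age-referenced actual-minus-predicted difference at the four treatment visits (6, 12, 18 and 24 weeks), not to raw change. As support, report the DSM-minus-CONV difference in gain for each 6-week block with its 95% confidence interval, from the time-by-condition model already planned. Note that CONV is an active, intensity-matched treatment, so this contrast subtracts its treatment response as well as growth. It belongs beside the age-referenced comparison and does not replace it.
2. Replace the last sentence of the rule with: *If the maximum is at 24 weeks, or the 95% CI for the 18-to-24-week gain does not exclude a prespecified meaningful further gain, the optimum is not identified within 24 weeks.* The sponsor must set that gain in advance on the scale used. A test of whether the point estimate is still rising would not do, because under a true plateau it rises about half the time.
3. Word the Aim 1 conclusion as time to plateau under continuous treatment, and limit statements about retention after stopping to the 24-week course.

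This needs no new data. The cost is a narrower claim and imprecise block estimates (half-widths of 0.9 to 2.9 points within DSM and 1.3 to 4.0 between arms, on the assumptions above). Even with a true 12-week plateau, the maximum falls at week 24 in 33% to 38% of simulated trials, so the answer would be *not identified* at least that often.
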